9.5 Safety Analysis

Analysis of the safety data will involve tabulating the occurrence of serious adverse events, adverse events, and unanticipated problems between the two groups (see 5.4 Safety Outcomes above).

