In addition to health services utilization costs associated with Usual Primary Care (UPC) for chronic pain, intervention costs in this arm will be minimal but will include training of UPC veteran participants and primary care staff on use of the Whole Health Resource Directory. For the WHT and PC-GE interventions, intervention costs will be calculated using a combination of VA administrative and clinical staff time devoted to each of the active interventions as well as costs associated with participant services utilization. Specifically, for the WHT intervention, visit costs will include team conferencing time and clinician time, including coach time (hourly rate for each team member) that will be ascertained using clinic visit notes in the electronic medical record (EMR) plus estimated administrative time for each clinical visit. PC-GE intervention costs will be estimated by accounting for the number of PC-GE modules for patient participants per site and the clinician and administrative time associated with each module. All other VA and non-VA community care healthcare costs will be collected using Decision Support Systems (DSS) National Data Extracts, the official cost managerial accounting system for VHA as well as new databases for computing costs for non-VA community care (after the Mission Act). These analyses will focus on VA and non-VA outpatient visits and outpatient pharmacy costs. Outpatient costs for the main analysis will be organized in the following groups by stop code field: integrative (CIH), primary care, emergency department, mental health, substance use disorder care, specialty pain care, ancillary, physical health specialty, and other. Outpatient VA medication costs will also be assessed using VA DSS data and will be divided by medication

class into opioid, non-opioid pain related, and other. We will also track inpatient admissions of all study participants during follow-up.

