Within 24 hours of the WHT visit, the study coordinator will call the participant to collect PEG and PHQ-4 data and will email the WHT this information via encrypted email. The WHT PCP will enter this information into the standard clinic note template in the EMR as health factors retrievable in VA administrative databases. In keeping with our pragmatic trial design, participants will be able to attend WHT visits in- person, by video telehealth, or telephone. The mode of intervention delivery for each participant will be captured through the clinic note templates as health factors retrievable through VA administrative databases.

**WHT motivational coaching protocol:** WH coaches will aim to conduct eight WH coaching sessions (following the initial session to complete the PHI) roughly weekly for the first few months and then provide participants the option of additional ‘booster’ coaching sessions which will be offered monthly for the remainder of the 12 months. WH coaches will provide patients support in pursuing, refining and tracking SMART goals and using communication techniques like MI, and examine barriers and ambivalence where appropriate. Coaching sessions will be guided by a structured EMR template (see Appendix 3C. Whole Health Coaching Note), and will be conducted by telephone or video telehealth, and last approximately 20-30 minutes.

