Within 24 hours of each PC-GE session, the study coordinator will call the participant to collect PEG and PHQ-4 data and will email the PC-GE provider this information via encrypted email. This data will then be entered by the MH provider in the clinic note template embedded in the VA EMR (see Appendix 4.0 PC-GE Clinic Note Templates). In keeping with our pragmatic trial design, participants will be able to attend group education sessions in-person, by video telehealth, or telephone, so groups may be mixed by intervention delivery mode. The mode of intervention delivery for each participant will be captured through the clinic note templates as health factors retrievable through VA administrative databases.

Psychologists or MH providers leading the group PC-GE sessions will be trained on the adapted protocol created for this treatment arm. The therapists will receive the VA's CBT-CP Therapist Manual ([name], Co-I) as a reference and additional resources to complement the adapted group therapy manual. As a part of training, clinician leads will also be provided with videos of patient-therapist vignettes demonstrating role-plays of common scenarios featuring a master trainer as the therapist and an actor as the patient). [name] will provide these trainings and will be available directly via email or telephone as needed for PC-GE consultation. Fidelity will be monitored by having all trained therapists document the intervention they deliver on a treatment fidelity checklist as a portion of the PC-GE group note template documentation. There will also be a monthly national case conference call where PC-GE providers will have a chance to review cases from the previous month.

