## 9.4 Reporting Procedures

Site PIs will be notified by the site project coordinator(s) immediately of any possible event that poses a risk to a subject. In addition, at least one of the PIs ([name] or [name]) or both will also be notified. The PI(s) will promptly respond to the problem and mitigate any negative consequences for the participant(s) involved. The PI and/or study coordinator will report the event to the IRB of Record within the timeline as follows:

a. **Unanticipated Problems Involving Risks to Subjects or Others.** Members of the VA research community are required to ensure that unanticipated problems involving risks to subjects or others in research are reported promptly to the IRB within five business days.

b. **Serious Unanticipated Problems Involving Risks to Subjects or Others.** Within five business days of becoming aware of any serious unanticipated problem involving risks to subjects or others in VA research, members of the VA research community are required to ensure that the problem has been reported in writing to the IRB.

c. **Local Unanticipated SAEs.** Within five business days of becoming aware of any local (i.e., occurring in the reporting individual's own facility) unanticipated SAE in VA research, members of the VA research community are required to ensure that the SAE has been reported in writing to the IRB.

If an AE/SAE is reported by a veteran directly to the local study coordinator at their participating site, the local study coordinator will complete an AE form on the study database within 24 hours of notification. If this event also meets the criteria for an SAE, the local study coordinator will indicate this on the AE form in the study database within 24 hours. For SAEs, the local study coordinator will download a pdf of the completed SAE form and send this as an attachment via encrypted email (see draft email A below) to the Project Manager, LSI, and Co-Principal Investigators Drs. [name] and [name]. The LSI and PIs will confer via email to determine the severity and relatedness of the event to the study intervention within 48 hours of notification. The Coordinating Center will follow VA Central IRB reporting guidelines as appropriate.

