2.3 Specific Aims

Aim 1: Conduct a multi-site pragmatic trial of Whole Health Team (WHT) vs. Primary Care Group Education (PC-GE) and both compared to Usual Primary Care in veterans with moderate to severe chronic pain. We hypothesize that WHT will be superior to PC-GE, and both will be superior to Usual Primary Care (UPC) with respect to the following outcomes:

H1.a. Improved pain interference at 12 months (primary outcome) and pain intensity, functioning, and quality of life (secondary outcomes).

H1.b. Decreased use of higher-risk pain medications, including opioids or high-risk combinations of pain medications (i.e., co-prescription of opioids and benzodiazepines) (secondary).

H1.c. Engagement in a greater number of non-pharmacological pain management activities (secondary).

H1.d. Improvement in mental health-related symptoms, including sleep problems and suicidality (secondary).

1. Randomization

The unit of randomization was the individual. Stratified block randomization with varying block sizes (24 or 48) was used. Participants were stratified by site, sex, and current opioid therapy and were randomized in an 11:11:2 (WHT:PC-GE:UPC) ratio. Allocation concealment was maintained through a module in Stata called "RALLOC".

2. Blinding

It is not possible to blind participants or those delivering the intervention to treatment assignment. However, we have blinded the study statistician, the PIs of the study, and those assessing patient reported outcomes will be blinded.

3. Outcomes

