7.1 General Considerations

The analysis of the primary and secondary outcomes will be according to the principle of intent-to-treat, i.e., participants will be analyzed according to their original treatment assignment regardless of adherence to the protocol. All analyses will account for the IRGT design and stratification by site, sex, and opioid use. The unit of analysis will be the participant. Three pairwise comparisons will be conducted: WHT vs. PC-GE; WHT vs UPC; PC-GE vs. UPC. SAS version 9.4 and the latest version of R will be used for analyses. Overall, family-wise type I error rates (two-sided) of 0.05 will be considered for both the primary and secondary outcomes split such that 0.03 will be given to the comparison between WHT and PC-GE and 0.01 will be given to each of the comparisons of PC-GE and WHT to UPC.

Comparability of treatment groups will be assessed by comparing the distribution of baseline characteristics in the three groups using appropriate graphical procedures and summary statistics (e.g., means and standard deviations for continuous data; frequencies and proportions for categorical data). The randomization is designed to produce balance on important covariates. Any baseline covariates that appear to be imbalanced between the treatment groups will only be adjusted for in sensitivity analyses.

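### SAP 9.5 tabulates harms for two groups in a three-arm trial, and does not separate events by how they came to light although the active arms have more study contacts than usual care

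*SAP*

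**What the plan says.** The safety analysis in SAP 9.5 is a single sentence. It describes "tabulating the occurrence of serious adverse events, adverse events, and unanticipated problems between the two groups" and refers back to SAP 5.4, which defines adverse and serious adverse events but names no groups.

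Elsewhere the SAP has three arms. Its Randomization section says that participants "were randomized in an 11:11:2 (WHT:PC-GE:UPC) ratio". SAP 7.1 describes "comparing the distribution of baseline characteristics in the three groups" and states: "Three pairwise comparisons will be conducted: WHT vs. PC-GE; WHT vs UPC; PC-GE vs. UPC".

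On how events are found, the Protocol gives several routes:

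- The schedule in Protocol 7.1 marks adverse events at 3, 6, 9 and 12 months, with no restriction by arm. Masked evaluators conduct those assessments (Protocol 7.2).
- Protocol 9.1 lists telephone assessments, PCP visits and intervention visits as places where mental health concerns may be raised.
- Protocol 9.4 provides for spontaneous reports: "If an AE/SAE is reported by a veteran directly to the local study coordinator at their participating site", that coordinator completes the AE form.
- Only the active arms have coordinator calls tied to visits. For WHT: "Within 24 hours of the WHT visit, the study coordinator will call the participant to collect PEG and PHQ-4 data". For PC-GE: "Within 24 hours of each PC-GE session, the study coordinator will call the participant".

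For all arms, Protocol 4.2 adds: "We will also track inpatient admissions of all study participants during follow-up".

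**The concern.** A two-group table cannot be produced from a three-arm trial without a decision that the SAP does not make. The analyst could drop UPC, combine the two active arms against UPC, or treat the wording as a slip and show three columns. Each gives a different account of harms. The trial hypothesises that both active arms are superior to UPC, so harms against UPC are needed next to benefit, for each active arm separately. The grouping should be fixed before anyone sees event data by arm.

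The second issue is ascertainment. SAP 5.4 records adverse events regardless of relationship to the intervention and includes passive suicidal ideation. An event of that kind is recorded only if the participant mentions it to someone on the study. Active-arm participants have many more occasions to do so, and neither SAP 5.4 nor SAP 9.5 distinguishes events by where they were reported.

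**Working it through.** SAP 9.5 gives no event rate, margin, alpha or power, so there is no safety figure to reproduce. The check has four steps.

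**1. Number of groups.** SAP Randomization: three arms. SAP 7.1, baseline: three groups. SAP 7.1, efficacy: three pairwise comparisons. SAP 9.5, safety: two groups, not named. The safety sentence disagrees with the rest of the SAP.

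**2. What a literal reading loses.** If UPC is left out:

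- planned sizes (SAP Sample Size: 341, 341 and 83, total 765): 83/765 = 10.8% of participants are missing from the table;
- actual total of 769 (SAP synopsis) at 11:11:2: 769 × 2/24 ≈ 64, and 64/769 = 8.3%.

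If the active arms are merged, no one is lost, but WHT and PC-GE can no longer be told apart.

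**3. Scheduled study contacts after baseline.** Optional boosters and the orientation call given to every arm are excluded. The Protocol text on WHT follow-up can be read as four or five team visits, hence the range.

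| | WHT | PC-GE | UPC |
|---|---|---|---|
| Intervention contacts | 1 health inventory + 8 coaching + 4 to 5 visits = 13 to 14 | 1 orientation + 5 modules + 1 discharge = 7 | 0 |
| Coordinator calls tied to visits | 4 to 5 | 7 | 0 |
| Masked assessments | 4 | 4 | 4 |
| Total | 21 to 23 | 18 | 4 |

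Active-arm participants also keep their usual primary care (Protocol 9.2), so these contacts are additional to those of UPC.

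**4. What that could do to a comparison.** Assume equal true risk. Let c be the share of events captured through the routes common to all arms, and e the share of the remainder that the extra contacts pick up. Then

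recorded ratio, active to UPC = [c + (1 − c)e] / c.

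The documents give neither c nor e. As an illustration only:

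| c | e = 0 | e = 0.25 | e = 0.75 |
|---|---|---|---|
| 0.9 | 1.00 | 0.925/0.9 = 1.03 | 0.975/0.9 = 1.08 |
| 0.7 | 1.00 | 0.775/0.7 = 1.11 | 0.925/0.7 = 1.32 |
| 0.5 | 1.00 | 0.625/0.5 = 1.25 | 0.875/0.5 = 1.75 |

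The direction follows from the contact counts if the extra contacts find anything at all. The size depends wholly on the two assumed shares.

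**The case against.** The strongest reply is that the wording is a drafting slip. SAP 7.1 shows that the authors know there are three groups, and the SAP contents list an appendix of DSMB tables that is not in the text available and may already have three columns. A slip is indeed the likeliest explanation, so the documents do not support inferring that UPC will be left out. The sentence is nonetheless the operative safety rule and should be corrected.

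On detection, the coordinator calls are described as collecting PEG and PHQ-4 data. Nothing says that they ask about adverse events. The scheduled collection is the same in all arms, spontaneous reporting is open to UPC participants, and PCP visits are a named source that UPC also has. All of this stands. It means that a bias is possible, not shown, and it may be close to nil for hospitalisations, which VA records capture in every arm.

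Three stronger readings are tempting and should be resisted.

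- A reader might infer that no fair statement on suicidality against UPC is possible. The documents contradict this. The PHQ-9 is given to every arm at every assessment (Protocol 7.2.4), follow-up is masked, and suicidality is a secondary outcome with pairwise 12-month contrasts that include UPC (SAP 5.3, 7.1 and 7.3).
- A reader might treat the unequal allocation as a source of bias. Raw counts do differ by arm size, but SAP 9.5 does not say that denominators will be omitted. Stating them settles the matter.
- A reader might conclude that the main comparison should use only events elicited at the masked assessments. That could reverse the bias. An active-arm event already logged by the local coordinator might not be mentioned again at the assessment, so it would drop out of the main table.

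**Conclusion.** SAP 9.5 is wrong as written. It specifies two unnamed groups in a three-arm trial and conflicts with SAP 7.1. Literal use would drop 8.3% to 10.8% of participants or merge arms. This rests on the text alone.

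The ascertainment point holds in a limited form. The active arms have 4.5 (18/4) to 5.75 (23/4) times as many scheduled study contacts as UPC, and the SAP does not separate events by route. A comparison with UPC over all sources may therefore be biased against the active arms, most plausibly for non-serious events and passive suicidal ideation. That sources will be mixed is inferred from the SAP's silence. The illustrative ratios of 1.00 to 1.75 rest on assumed capture shares and are not an estimate for this trial. The point is worth correcting, but it does not undermine the trial's ability to report on harms.

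**What to change.** Amend SAP 9.5 as follows.

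1. Replace the two groups with the three randomised arms: WHT, PC-GE and UPC. For SAEs, AEs and unanticipated problems, report participants with at least one event (n/N, %) and the number of events in each arm.
2. Keep the table of events from all sources as the main display, so that no event is lost.
3. Add a supportive table by route of detection, scheduled 3-, 6-, 9- or 12-month assessment versus any other contact, where the AE record or its dates allow. Report how many events cannot be classified.
4. Compare hospitalisations across arms from the VA inpatient data already tracked for all participants.
5. For suicidality, cross-refer to the masked PHQ-9 comparison under SAP 7.3.
6. State in the text that contact frequency differs by arm, so that readers can weigh the comparison with UPC.

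The cost is a few lines of SAP text and some extra tabulation. The supportive table may be incomplete: under both reporting routes in Protocol 9.4 the local coordinator completes the AE form, and the documents do not show a field for source. The SAP cover page allows changes up to final data lock and before unblinding, and the change should be made within that window.

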9.6 Missing data

Several strategies will be imposed to accommodate the likelihood that missing data will occur during the study. Prevention is the most obvious and effective manner to control bias and loss of power from missing data. We will follow the intent-to-treat principle, requiring follow-up of all participants enrolled regardless of the treatment received. Timely data entry combined with quarterly missing data reports will trigger protocols for tracking and obtaining missing data. Despite these efforts, it is reasonable to assume missing data will occur. Our primary analysis is valid under the assumption that missing data are missing at random (MAR). We will evaluate the plausibility of this assumption by determining the extent of missing data and using logistic regression to identify factors associated with missing data. If we find baseline factors associated with missingness, then we will conduct sensitivity analyses to investigate the effect of including those factors as covariates in the models evaluating the difference between groups. As a second sensitivity analysis under the MAR assumption, we will use multiple imputation based on chained equations (which can accommodate both continuous and categorical variables) to impute missing variables. We will conduct sensitivity analysis using pattern-mixture models and multiple imputation under missing not at random (MNAR) assumptions to examine the robustness of conclusions of the primary analysis to missing data. The multiple imputation under MNAR will assume that those who drop out have worse outcomes than those who stay in the study.¹⁸ We will also consider inverse probability weighting to account for missing data, if necessary.

References

